5.5 Study Evaluations

All potential participants will be screened for eligibility as described above for inclusion/exclusion criteria using medical charts and collection of general history information related to cancer diagnosis, treatment, dysphagia treatment, and current swallowing problems. Once deemed eligible, the participants will then undergo evaluation to determine eligibility for RST that includes an MBSS with simultaneous respiratory recordings, completion of cognitive screen (MoCA) (Appendix), and questionnaire (MDADI) (Appendix).

If participants meet eligibility criteria to participate in RST as outlined above, each participant will undergo in-clinic RST sessions with an SLP. After the RST is completed, participants will undergo an MBSS with simultaneous recordings, completion of MDADI, and information about oral intake/diet tolerance (FOIS) (Appendix) for post-treatment measurements. Further, the participant will undergo these same procedures at 1-month, 3-months, and 6-months after experimental portion is completed.

5.6 Data Analysis

Statistical Considerations. Specific Aim 1: Trial design. The primary objective of Specific Aim 1 is to demonstrate the clinical efficacy and durability of RST in participants with dysphagia with a history of OP HNC. A total of 88 participants will be [recruited and randomly assigned 1:1 to either RST (intervention arm) or control arm, given the crossover design of the study. We will use a stratified permuted block randomization scheme with random block sizes of 2 or 4 to balance important prognostic variables across the two trial arms. There will be 5 strata defined by treatment modality (radiation therapy alone, surgery alone, chemo-radiation therapy, surgery + post-operative radiation therapy, surgery + post-operative radiation therapy + adjuvant chemotherapy). The study statistician will maintain randomization lists and be responsible for randomizing consented participants. The study schema is depicted in Figure 8. The control arm will cross over to RST after visit 1 following data collection for evaluation of clinical efficacy.

Endpoint Definitions and Analysis Plans. The primary efficacy endpoint for Aim 1 is oropharyngeal swallowing physiologic metrics (MBSImp) and evaluated at: visit 0, defined as pre-RST for intervention subjects, and baseline for control subjects; and visit 1, defined as post-RST for intervention subjects or 4 weeks post-baseline evaluation for control subjects. We will compare changes in MBSImp physiologic function metrics in patients randomized to intervention versus control. Change in MBSImp physiologic function metrics will be compared using one-way analysis of covariance (ANACOVA), with trial arm as the main effect and adjustment for stratification variable of treatment type. If approximate normality is not satisfied, we will use generalized estimating equations (GEEs) with an identity link function and robust standard error estimator. Furthermore, the regression framework of GEEs will accommodate adjustment for stratification factor. Durability of response will be evaluated using ANACOVA or GEEs as described by comparing post-RST MBSImp physiologic function metrics to those obtained at 1-, 3-, and 6-month follow-up visits. We will further evaluate the modifying and confounding effects of sex, age, smoking status, COPD status, and pulmonary function.

[figure not shown]

Figure 7 Study schema for current proposal.

Further, response durability will be evaluated using FOIS measures obtained at 1-, 3- and 6-months post-RST. Because control subjects cross over to RST at visit 1, FOIS measures collected at visit 1 for control subjects additionally will serve as their pre-RST FOIS measures (Figure 7). Clinical efficacy will be evaluated by comparing change in FOIS (Δ FOIS = FOIS_{visit1} – FOIS_{visit0}) in patients randomized to intervention versus control. Δ FOIS comparisons will be conducted using one-way analysis of covariance (ANACOVA), with trial arm as the main effect and adjustment for stratification variables. If approximate normality is not satisfied, we will use generalized estimating equations (GEEs) with an identity link function and robust standard error estimator, which accommodates valid inference in the presence of misspecification.^{103,104} Furthermore, the regression framework of GEEs will accommodate adjustment for stratification factors. Durability of response will be evaluated using ANACOVA or GEEs as described by comparing post-RST FOIS measurements to those obtained at the 1-, 3- and 6-months follow-up visits. In addition, we will model longitudinally collected FOIS scores as a function of time (measured as a categorical variable) using GEEs, with additional independent variables for stratification factors and pre-RST FOIS included in all models. Comparisons at individual time points will be performed using model-based linear contrasts with inference based on associated two-sided generalized score tests. We will further evaluate the modifying and confounding effects of sex, age, smoking status, COPD status, and pulmonary function. Secondary endpoints include MDADI summary scores, and respiratory-swallow phase patterns (binary measure classified as optimal versus non-optimal) collected at all time points. Analysis of MDADI scores will follow the approach used to analyze FOIS scores. Comparisons between visits 0 and 1 respiratory-swallow phase patterns will be performed using a Rao-Scott chi-square test, an approach that accommodates comparisons of proportions from paired data with Mantel-Haenszel-type adjustments for stratification factors.¹⁰⁵ GEE models of respiratory-swallow phase patterns will be similar to those described for FOIS measures but using instead a

logit or probit link function as appropriate for binary endpoints. Results for all endpoints will be summarized separately for males and females to assess differences by patient sex.

Statistical Considerations: Specific Aim 2 Design and Methods – Intervention Impact of RST on Swallowing Physiology. We will elaborate the treatment impact of RST by detailing the physiological, airway protective and morphometric changes that occur from the intervention. We will use MBSImP, PAS (described for Aim 1), and CASM.

MBSImP Scores. The MBSImP scores will provide a primary outcome measure of swallowing impairment. The MBSImP is a validated and reliable scoring system for the quantification of swallowing impairment from MBSS recordings.^{13,14,19} This tool has an ordinal scoring schema that permits quantification of oral, pharyngeal, and esophageal components of swallowing physiology. The operational definitions for the component scores represent a unique and unambiguous observation of structural movement and bolus flow. Seventeen physiologic components will be scored on a previously validated, rank order scale from least to most impaired. The scale for components ranges from 0-2 to 0-4 for each physiologic component.¹⁴ Years of field testing shows scores of 0 or 1 for the physiologic components of lip closure, oral residue, pharyngeal residue, and tongue base retraction are considered to be within normal limits.¹¹² For all other components, scores greater than 0 represent some level of impairment. Two methods will be used for MBSImP scoring: swallow-by-swallow (SS) and overall impression (OI). SS scoring assigns an MBSImP score for all applicable physiologic components for each of the 12 swallowing tasks given during the protocol. SS cores will be recorded for each participant. The highest (worst) score will be given during SS scoring when the participant's condition or performance on a previous swallowing task results in the withholding of a subsequent swallowing task for safety concerns.^{9,52} Additionally, missing data in SS interpretation will result if a participant refuses a swallowing task.⁵² As such, we will only include scores for swallowing tasks that are actually presented.

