A total of 51 participants will be recruited with the goal of 40 participants enrolled. Participants will be randomly assigned 1:1 to either RST (intervention arm) or no active treatment (control arm), which is considered standard of care in this patient population. The participants in the control arm will have no active treatment for 4 weeks and will then participate in RST as a cross-over design. Data obtained will be used to evaluate clinical efficacy and durability. The primary efficacy endpoint is physiologic function metrics of the oropharyngeal swallow, and the secondary endpoint will be respiratory-swallow phase patterning. We will also elaborate on the impact of RST by detailing the physiological, airway protective, and morphometric changes that occur. We will use reproducible, reliable, and validated metrics that include the Modified Barium Swallow Impairment Profile, Penetration-Aspiration Scale, and Computational Analysis of Swallowing Mechanics to distinguish the mechanistic effects of RST. Further, adherence to a novel HP component using self-guided practice will be introduced and tested for feasibility and contribution to the degree and durability of the RST intervention effect.

Our overarching goal is to provide two parallel tracks of knowledge generation: 1) provide immediate clinical translation of experimental findings to improve the lives of Veterans and non-Veterans, and 2) drive model generation on fundamental mechanisms of motor coordination. Basic knowledge will drive clinical application and vice-a-versa. As such, this is an ideal experimental and clinical context that will fuel knowledge generation in this highly significant area of science and clinical practice.

Clinical Impact of Respiratory-Swallow Training on Refractory Dysphagia in OP HNC Funding
(1010498-19)

Specific Aim 1. Directly train optimal respiratory-swallow phase patterning using RST and test the clinical efficacy and durability of the effect measured by change in physiologic metrics of the oropharyngeal swallow. Hypothesis: RST will improve swallow physiology, oral intake status and liquid/food texture tolerances. Primary Outcome: Physiologic metrics of the oropharyngeal swallow as measured by the Modified Barium Swallow Impairment Profile (MBSImP) scores,^{13,14,19}; Secondary Outcome: Functional Oral Intake Scale (FOIS).^{17,18}

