5.0 Study Procedures

5.1 Study Design

Specific Aim 1 – Respiratory-Swallow Training (RST) In-Clinic.

Patient Sample. A total of 51 participants will be enrolled with the goal of 40 recruited if they meet inclusion criteria. Forty participants will be randomly assigned (1:1) to either RST (intervention arm) or no active treatment (control arm), which is considered standard of care in this patient population. Participants assigned to the control arm will cross-over after 4 weeks of no active treatment to undergo RST. All patients will participate in a pre-RST MBSS. The purpose of this pre-RST MBSS is to identify their baseline pre-RST respiratory-swallow phase patterning by specifying the respiratory phase and volume at time of swallowing initiation, assess swallowing physiology (MBSImP) and assess clinical swallowing status (FOIS). Participants will be included in the study if they are able to swallow at least one liquid consistency without visible tracheal residue (PAS ≤ 6) and without the use of a compensatory strategy or swallow maneuver. Participants will be excluded if they have known allergy or dietary restriction for contrast materials or liquids used during the MBSS or training, currently drinking greater than two drinks per day, severe COPD, are unable to swallow one liquid consistency without the use of a compensatory strategy or swallow maneuver without aspiration, or history of aspiration pneumonia within the past 12 months.

Clinician Examiners, Raters and Trainers. Expert speech-language pathologists (SLPs) will participate in this study to provide RST training, conduct the MBSSs, and perform blinded MBSImP and PAS scoring (i.e., without benefit of patient identifiers, randomization, clinical information, and performance during RST). The SLPs will not crossover study roles.

Spirometry. All Veteran and non-Veteran participants will undergo PFTs using spirometry performed by American Thoracic Society standards to stage COPD.⁸⁸ Participants will be characterized into Global Initiative for Obstructive Lung Disease (GOLD) spirometric groups on the basis of % predicted FEV1.⁹⁰ Any patient with severe stage COPD will be excluded from the study to protect against risk since experience in our clinic and previous study showed these patients could not consistently perform the proposed training tasks.

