Data Management, Analysis, and Reporting System Overview. Study related data are stored on VA approved computers and the VA research shared drive (S:), including de-identified study-related data (videofluoroscopic images, respiratory traces). Identifiable data (VASA), including demographic data, questionnaire responses, and treatment results are stored on the VA REDCap behind the VA firewall. De-identified videofluoroscopic images and respiratory tracings will be transported via VA issued encrypted external hard drives for analysis by specially trained analytic experts to the PI's lab at Northwestern University, and then stored on and analyzed from a password protected, dedicated server. This server is managed by Northwestern Information Technology and accessible to only approved study personnel. We will update the data transfer and storage operations as we are provided additional guidance and requirements from the ORO, Office of Research Oversight.

Power and Sample Size Justification. A total of 40 subjects will be randomized 1:1 using stratified block randomization to either Respiratory-Swallow Training (RST, intervention arm) or no control arm, where the participants serve as their own control and then cross over into the intervention group. Strata will be defined by treatment type. Data obtained will be used to evaluate clinical efficacy and durability. The primary outcome measure will be MBSImp physiologic function metrics of the oropharyngeal swallow. Our previous preliminary trial that tested the safety and efficacy of the behavioral swallowing intervention in a small sample of Veteran and non-Veteran patient with head and neck cancer showed a positive change in the physiologic outcomes. Assuming a similar treatment effect in the current trial, 20 patients in each arm provides 95% power to detect a change in MBSImp physiologic function in at least one of three MBSImp components (laryngeal vestibular closure, tongue base retraction, and pharyngeal residue) based on a Cochran-Mantel-Haenszel test with two-sided $\alpha = 0.025$. Although dropouts have been rare in our prior studies, we nonetheless inflated our sample size by 10% to adjust for unanticipated attrition, and plan to recruit 20 participants per arm for a total sample size of 40 subjects to guarantee at least 80% power. Thus, our final sample size will be a total of 40 participants.

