Termination. If a participant does not meet a single target goal following 3 sessions, the RST intervention will cease, and data will contribute to the intention-to-treat analysis as outlined in the research plan.

Non-participation. Each participant has the alternative to not participate in the study. If the participant chooses not to participate, it will not affect their current and/or future medical care or any benefits to which they are entitled.

Human Subjects Involvement and Characteristics

A total of 51 Veteran and non-Veteran volunteers will be recruited.

Inclusion of Women, Minorities and/or Children. *No participants will be excluded based on sex or race/ethnic origin*. Sex, ethnic, and racial information will be collected as part of the demographic information. Participants will be selected based on the inclusion criteria identified above.

Ethnicity (i.e., Hispanic/Latino, Non-Hispanic/Latino) will be recorded separately from race. All applicable racial categories (i.e., American Indian/Alaskan Native, Asian, Native Hawaiian or other Pacific Islander, Black/African American, White) will be recorded for each participant by study personnel. All ethnic and racial totals will be reported, including specific categories for those participants who report mixed racial descent (any combinations recorded by study personnel). No outreach program to recruit minorities is planned because all eligible individuals, regardless of race or ethnic origin, will be invited to participate. Historic data indicates men are twice as likely to have OP HNC compared to women.⁴ Recent studies from three countries (United States, United Kingdom, and Romania) suggest there is a 2:1 ratio of males to females diagnosed with HNC and make up 80% Caucasian, 11% Black/African American, 4% Hispanic, and 5% other racial/ethnic categories.¹²²⁻¹²⁴ It is anticipated that the sex, ethnic and racial mix of this study sample will roughly parallel these demographic data.

ANTICIPATED TARGETED/PLANNED ENROLLMENT: Number of Subjects			
Ethnic Category	Sex		
	Females	Males	Total
Hispanic or Latino	0	3	3
Not Hispanic or Latino	2	35	37
Ethnic Category: Total of All Subjects *	2	38	40
Racial Categories			
American Indian/Alaska Native	0	0	0
Asian	0	0	0
Native Hawaiian or Other Pacific Islander	0	0	0
Black or African American	0	6	6

White	2	32	34
Racial Categories: Total of All Subjects *	2	38	40

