Children will not be eligible for enrollment in this project. Children do not commonly present with HNC. Further, respiratory-swallow phase patterns and training have not been systematically studied in dysphagic children. This supports their exclusion from this project that is based on preliminary data acquired in adults.

5.2 *Recruitment Methods*

A total of 51 Veteran and non-Veteran volunteers will be enrolled with the goal of 40 meeting inclusion criteria. Potential participant volunteers will be identified by the following methods of participant recruitment, all approved by the VA Institutional Review Board (IRB): 1) follow-up medical visits, particularly the otolaryngology-head and neck clinics; 2) announcement of the study in the VA patient bulletins and monitors (Appendix); 3) community-based outpatient clinics (CBOCs); and 4) review of patient medical charts (CPRS) at Hines VA to find patients that match the diagnosis of oropharyngeal cancer and dysphagia diagnoses (letters will be mailed to these potential patients with information in regards to the study. Also included will be a brief survey, along with a postage paid return envelope, which allows the patients to indicate if interested in participating or not); 5) posting of recruitment flyers at Jesse Brown VA, Loyola University Medical Center, Northwestern Memorial Hospital, University of Chicago Medical Center, and Northwestern Medicine Healthcare Partners.

Participants will be compensated for their participation in the study to assist support of their time and travel. Participants will receive \$40 for each MBSS and \$30 for each RST session. For participants randomized to immediately undergo the intervention, they have the potential maximum of earning \$440. The participants randomized to the control group will undergo one additional MBSS procedure immediately prior to their cross-over to the intervention arm, for a potential maximum of \$480. Participant payment will be made according to the current local fiscal office guidance and processes. Planned payments will be approved by appropriate study personnel for disbursement according to this schedule:

- Payment 1: after first study visit to determine eligibility for intervention (which includes first MBSS)
- Payment 2: after week 1 of intervention
- Payment 3: after week 2 of intervention
- Payment 4: after week 3 of intervention
- Payment 5: after week 4 (final) of intervention
- Payment 6: after post-intervention study procedures

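### Section 5.6 says 88 participants are randomised; the abstract and every design, power, enrolment and recruitment statement set 40

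*Combined protocol and SAP*

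**What the plan says.** Six places in the combined protocol and SAP bear on the planned sample size.

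- **Section 5.6, Data Analysis (Specific Aim 1, trial design):** "A total of 88 participants will be [recruited and randomly assigned 1:1 to either RST (intervention arm) or control arm". The sentence goes on to mention the cross-over design, but gives no calculation.
- **Section 5.1, Patient Sample:** "Forty participants will be randomly assigned (1:1) to either RST (intervention arm) or no active treatment (control arm").
- **Section 5.1, Power and Sample Size Justification:** "A total of 40 subjects will be randomized 1:1 using stratified block randomization". After describing 20 per arm and a 10% allowance for attrition, the paragraph ends: "Thus, our final sample size will be a total of 40 participants".
- **Section 5.1, planned-enrolment table** (headed "ANTICIPATED TARGETED/PLANNED ENROLLMENT: Number of Subjects"): 2 females and 38 males, total 40.
- **Section 5.2, Recruitment Methods:** "A total of 51 Veteran and non-Veteran volunteers will be enrolled with the goal of 40 meeting inclusion criteria".
- **Abstract:** "A total of 51 participants will be recruited with the goal of 40 participants enrolled".

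The figure 88 appears only in Section 5.6.

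**The concern.** The number to be randomised is a core design parameter, and Section 5.6 is where a statistician, a monitoring board or a journal would look for it. The same paragraph sets the strata and block sizes and makes the study statistician responsible for the randomisation lists. Read alone, it gives a total that the power statement does not support. Accrual measured against it would look less than half complete when the trial had in fact finished, and a final report could quote either 40 or 88 as the planned size. Nothing is claimed about allocation: permuted blocks of 2 or 4 work for either total.

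**Working it through.** **Inputs.** 88 randomised 1:1 (Section 5.6). 40 randomised, 20 per arm, 10% attrition allowance, two-sided alpha 0.025 (Section 5.1, power paragraph). 51 recruited or enrolled (abstract, Sections 5.1 and 5.2). 2 females and 38 males (planned-enrolment table).

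**1. Reproduce the 40.** 2 arms × 20 = 40. The table gives 2 + 38 = 40. The power paragraph says the 10% allowance is already included. It shows no starting number, but 18 per arm would fit: 18 / 0.90 = 20.

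**2. Size of the conflict.**

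- Difference: 88 − 40 = 48.
- Ratio: 88 / 40 = 2.2.
- Per arm: 88 / 2 = 44 against 20.
- Completing 40 as a share of 88: 40 / 88 = 45%.

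**3. Can 88 be reached from the stated inputs?**

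| Reading | Calculation | Result |
|---|---|---|
| Volunteers recruited | stated | 51 |
| 40 with 10% attrition | 40 × 1.10; 40 / 0.90 = 44.4 | 44 or 45 |
| 51 with 10% attrition | 51 × 1.10 = 56.1; 51 / 0.90 = 56.7 | 57 |
| Participant-periods under cross-over | 20 × 1 + 20 × 2 | 60 |
| The same with 10% | 60 × 1.10; 60 / 0.90 = 66.7 | 66 or 67 |

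None gives 88. One calculation does: 2 × 40 × 1.10 = 88. It needs either 40 per arm or two periods in both arms. The power paragraph states 20 per arm, and only the control arm crosses over, so the intervention arm has one period. The documents do not offer this as a derivation.

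**4. Could 88 be a power-based number?** This check is indicative only. It takes the preliminary pre- and post-training impairment rates (Section 2.0, Table 3) as control and RST rates, with one observation per patient. These are assumptions. With n per arm, p̄ the mean of the two rates and z = 2.241 for two-sided 0.025:

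Power = Φ{[|p1 − p2| − z√(2p̄(1 − p̄)/n)] / √([p1(1 − p1) + p2(1 − p2)]/n)}

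For laryngeal vestibular closure at n = 20: p1 = 0.782, p2 = 0.555, difference 0.227, p̄ = 0.6685. The null standard error is 0.149 and the alternative standard error 0.144. So (0.227 − 2.241 × 0.149) / 0.144 ≈ −0.74, and power is 23%.

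| Component (rates) | 20 per arm | 44 per arm |
|---|---|---|
| Laryngeal vestibular closure (78.2% to 55.5%) | 23% | 51% |
| Tongue base retraction (96.0% to 88.6%) | 8% | 17% |
| Pharyngeal residue (96.1% to 88.4%) | 9% | 18% |
| At least one, if independent | 36% | 67% |

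"At least one" is 1 minus the product of the three values of (1 − power). Neither total reproduces the stated 95%, so this check gives no support to 88. Nor does it verify the power claimed for 40; that is a separate question and does not bear on the contradiction.

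**The case against.** The strongest reply is that the intended number is obvious. Five places say 40 and one says 88, beside an unclosed bracket that suggests leftover text. No endpoint, test, alpha level or analysis population changes, so the harm is confined to reporting. That limits the consequence, and the leftover-text explanation is plausible though it is inference. It does not remove the conflict: the figure is current text, in the statistical section, and more than double the justified number.

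Two further points have some force. First, the power paragraph is not clean. It claims 95% power at 20 per arm, then says the sample was inflated by 10%, and still arrives at 20 per arm with at least 80% power, without showing a pre-inflation figure. So 40 is the number the plan states consistently and ties to a power claim, but its derivation is not shown. Second, Section 5.1 (Analysis Populations) replaces some early withdrawals. If those follow randomisation, the number randomised could exceed 40. This cannot explain 88: with 51 recruited, the excess could be at most 51 − 40 = 11.

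**Conclusion.** The contradiction is real and should be corrected. Section 5.6 states 88 randomised where the rest of the plan states 40: 48 too many, 2.2 times the target, 44 against 20 per arm. This follows from the documents' own statements and needs no outside figure. That 40 is the intended number rests on its agreement across five places and on its being the only total with a stated justification; the sponsor should confirm it. The finding is an internal inconsistency. It does not imply bias or an allocation fault, and it does not say that 40 is adequately powered.

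**What to change.** In Section 5.6, replace 88 with 40 randomised, 20 per arm, once the sponsor has confirmed that 40 is intended. Use one statement throughout: 51 are recruited and screened so that 40 are randomised. It would help to add whether replaced participants count towards the 40.

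Two clerical corrections belong in the same amendment:

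- Align the terms for the 51 and the 40. The abstract has 51 recruited and 40 enrolled, Section 5.1 (Patient Sample) reverses the two words, and Section 5.2 has 51 enrolled.
- In the power paragraph, the second arm is described as "or no control arm, where the participants serve as their own control and then cross over into the intervention group". Replace this with the no-active-treatment control arm defined in the abstract and in Patient Sample.

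The cost is a wording amendment only. No procedure, analysis or data collection changes.

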Inclusion and Exclusion Criteria. **Entry inclusion criteria:** 1) ≥ 21 years of age; 2) signed informed consent; 3) at least 6 months post head and neck cancer treatment for oral cancer, oropharyngeal cancer, laryngeal cancer, or hypopharyngeal cancer; 4) consumes ≤ 2 alcoholic drinks daily and 5) English speaking. **Entry exclusion criteria:** 1) known allergy or dietary restriction for materials used during the exam; 2) severe chronic obstructive pulmonary disease (COPD); and 3) recent history of aspiration pneumonia (past 12 months). **Intervention inclusion criteria:** 1) pass Montreal Cognitive Assessment (MoCA) (≥ 26)⁸⁷. **Intervention exclusion criteria:** 1) fails MoCA (< 26); and 2) inability to tolerate at least one liquid consistency (PAS ≥ 7). Women of child-bearing age will be screened via questionnaire in accordance with VA Medical Center policy precautions. Women who are pregnant will be excluded from this trial given that five MBSSs are required and the risk of any radiation to the fetus exceeds the potential benefit of this study. Men will also be counseled regarding the risks of radiation exposure to their reproductive organs. Hospital policy precautions for radiation safety will be applied. Informed consent will be obtained by the examining speech-language pathologist (SLP). The study procedures, potential risks, and benefits will be explained to all participants, and caregivers when appropriate, by the examining SLP. It will be explained that participation in the study will not have any impact on the quality of his/her present and/or future care as a patient. Further, if a participant chooses not to participate or drops out of the study at any time, there will be no consequences of this action. There will be no additional study sites involved with this research.

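### Block sizes of 2 or 4 are printed in the protocol of a trial whose arms staff can see, so an observer who tracks allocations could predict many of the next ones

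*Combined protocol and SAP*

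**What the plan says.** Section 5.6 (Statistical Considerations, Specific Aim 1) describes 1:1 allocation by a "stratified permuted block randomization scheme with random block sizes of 2 or 4". On strata it says: "There will be 5 strata defined by treatment modality". On custody it says: "The study statistician will maintain randomization lists and be responsible for randomizing consented participants". It does not say how often each block size is used, and nothing in the protocol withholds the sizes from enrolling staff.

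The comparison is training against no active treatment, with controls crossing to RST after 4 weeks (section 5.1, Patient Sample). The only outcome assessment described as blinded is that of the speech-language pathologists (SLPs) who "perform blinded MBSImP and PAS scoring". The same paragraph of section 5.1 bars SLPs from changing roles.

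Several roles take consent. Section 5.1 (Recruitment and Informed Consent) lists the principal investigator, the coordinator, the research SLP and clinical SLPs. Section 5.3 gives a similar list, and section 5.4 names the examining SLP. Section 5.4 also states "There will be no additional study sites involved with this research", although section 5.1 offers training at two locations.

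The number randomized is 40 in section 5.1 but 88 in section 5.6. That must be reconciled, but it hardly affects this point.

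**The concern.** Permuted blocks force the arms back to balance at the end of each block. Someone who knows the possible sizes and the earlier allocations in a stratum can work out the odds for the next participant. Here the sizes are printed in the document staff work from, the arm is evident from whether a participant starts training, and the stratum is known from the cancer treatment history before anyone is approached.

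Foreknowledge matters because it can influence who is approached, when consent is sought, and how a borderline case is handled. In a trial of about 40, a few such decisions could shift the comparison. Blinded scoring protects the rating of the swallow studies, not entry to the trial. The primary model in section 5.6 adjusts for treatment type and does not name baseline MBSImP as a covariate, so a baseline difference arising this way would not automatically be adjusted for.

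**Working it through.** The plan gives no predictability figure, so there is none to reproduce.

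**Inputs from section 5.6:** block sizes 2 or 4, ratio 1:1, five strata. With 40 participants (section 5.1) the average is 40/5 = 8 per stratum; with 88 it is 17.6.

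**Assumption not in the documents:** each block has size 2 with probability q. Base case q = 0.5, range 0.25 to 0.75.

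**Observer:** knows the sizes, q and every earlier allocation in the stratum, but sees no block boundaries.

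**First steps at q = 0.5**
- 1st allocation: 0.50.
- 2nd: opposite to the 1st with probability 0.5 × 1 + 0.5 × 2/3 = 0.833.
- 3rd: the first two are alike with probability 0.5 × 1/3 = 0.167. The block must then have size 4, and both the 3rd and the 4th are certain. Otherwise the 3rd is 50:50.
- 4th, when the first two differed: the posterior for size 2 is 0.5/0.833 = 0.6, so the 4th is opposite to the 3rd with probability 0.4 × 1 + 0.6 × 0.833 = 0.90.

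**All eight positions,** by exact enumeration of histories:

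| Position | Share predictable at ≥ 0.80 | Share certain |
|---|---|---|
| 1 | 0 | 0 |
| 2 | 1 | 0 |
| 3 | 0.167 | 0.167 |
| 4 | 1 | 0.167 |
| 5 | 0.083 | 0.083 |
| 6 | 1 | 0.083 |
| 7 | 0.125 | 0.125 |
| 8 | 1 | 0.125 |

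Predictable at ≥ 0.80: (4 + 0.167 + 0.083 + 0.125)/8 = 4.375/8 = 54.7%. Certain: 2 × 0.375/8 = 9.4%. Best-guess accuracy is 71.4%, against 50% by chance.

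**Sensitivity to q (8 per stratum)**

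| q | ≥ 0.80 | Certain | Best guess right |
|---|---|---|---|
| 0.25 | 31.4% | 12.9% | 70.6% |
| 1/3 | 39.7% | 11.7% | 70.7% |
| 0.5 | 54.7% | 9.4% | 71.4% |
| 2/3 | 53.4% | 6.8% | 72.3% |
| 0.75 | 52.7% | 5.3% | 72.8% |

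The 2nd allocation has probability q + (1 − q) × 2/3, which reaches 0.80 only when q ≥ 0.4. This explains the drop at low q. At q = 0.25 the share at ≥ 0.75 is still 56%.

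**Sensitivity to threshold (q = 0.5):** 54.7% at ≥ 0.80, 39.1% at ≥ 0.85, 21.5% at ≥ 0.90.

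**Sensitivity to stratum size (q = 0.5, ≥ 0.80):** 54.1% at 17 to 18 per stratum (total 88), about 52% for illustrative uneven strata totalling 40, and 45% for a stratum of 5.

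**Alternative, sizes 4 and 6 equally likely, 8 per stratum:** 26.7% at ≥ 0.80, 5.9% certain, 66.8% best guess right.

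**Arm-size imbalance, five strata of 8:** with sizes 2 and 4, a stratum ends two apart with probability 0.104 and is otherwise level. The variance of the total difference is 5 × 4 × 0.104 = 2.08, so the SD is 1.44. With sizes 4 and 6 the enumeration gives 2.38.

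**The case against.** The strongest reply is that predictability is not bias and that the plan has real safeguards. The statistician holds the lists and randomizes after consent. Eligibility rests on fixed cut-offs for cognition, FEV1 and the Penetration-Aspiration Scale. SLP roles are kept separate and scoring is blinded. Recruitment partly runs through mailed letters, bulletins and flyers, which narrows discretion over who is approached. Controls receive RST after only 4 weeks, so the motive to steer a patient is weak. Small blocks were chosen to keep the arms balanced, and moving to sizes 4 and 6 lowers guess accuracy by only about 4 points (71% to 67%).

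Most of this stands and limits the risk. It does not remove it. A list held elsewhere does not prevent inference from past allocations, and the inference can be made before anyone is approached. The role rule covers SLPs only, not the principal investigator or coordinator, who also take consent; section 8.0 has both meeting regularly with the research SLP about accrual. Randomizing only after eligibility seems intended, since section 5.1 has 51 entering and 40 randomized, but no section states the order.

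Some stronger readings go too far. A reader might infer that two like allocations in a row always settle the next. That holds only within one block: in AB followed by BA, the two Bs span a boundary that staff cannot see. A reader might also infer that no analysis could correct the resulting bias. Imbalance in a measured baseline can be adjusted for, and section 5.6 already includes pre-RST oral intake score in its longitudinal models for that scale; selection on unrecorded traits could not be adjusted for.

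**Conclusion.** The point holds as a minor design weakness. With the printed sizes, an observer who tracks allocations by stratum could predict about 55% of them with at least 80% probability if both sizes are equally likely, and 31% to 55% over the range of weights examined. Best-guess accuracy of 71 to 73% depends little on that weight. Certainty arises in about 5 to 13% of allocations.

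The figures assume about eight participants per stratum and an observer who knows every earlier allocation in it. They measure opportunity only. A reader might infer that recruitment has been or will be steered; the documents give no sign of this, and no effect on the primary endpoint can be estimated from them. Nor do they use the terms open-label or single-centre: visibility of the arms follows from the no-treatment control, and training may take place at two locations.

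**What to change.** For allocations not yet made:

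1. Remove the block sizes from the protocol and hold them in a document restricted to the statistician. The present sizes have already been disclosed, so the new ones should not appear in the amendment.
2. Drop size 2 and generate a new list within the same five strata, for example with random sizes 4 and 6. The 27% and 67% above assume that the observer knows those sizes.
3. State in section 5.6 that an allocation is released only after all eligibility results and the visit 0 swallow study are recorded.

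The parts work together, since changing sizes alone gains little on average guess accuracy. The cost is a short protocol amendment, a new list, and a larger chance difference between arm sizes: SD about 2.4 instead of 1.4 participants in a trial of 40.
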